### **5.8.2 Withdrawal from the Trial**

A subject must be withdrawn from the trial if the subject or subject's legally acceptable representative withdraws consent from the trial.

If a subject withdraws from the trial, they will no longer receive trial treatment or be followed at scheduled protocol visits.

Specific details regarding procedures to be performed at the time of withdrawal from the trial including the procedures to be performed should a subject repeatedly fail to return for scheduled visits and/or if the study site is unable to contact the subject, are outlined in Section 7.1.4 – Other Procedures.

## **5.9 Subject Replacement Strategy**

A subject who discontinues or withdraws from the trial will not be replaced.

## **5.10 Beginning and End of the Trial**

The overall trial begins when the first subject (or their legally acceptable representative) provides documented informed consent. The overall trial ends when the last subject completes the last study-related phone-call or visit, withdraws from the trial or is lost to follow-up (i.e. the subject is unable to be contacted by the investigator).

## **5.11 Clinical Criteria for Early Trial Termination**

The clinical trial may be terminated early if the extent (incidence and/or severity) of emerging effects/clinical endpoints is such that the risk/benefit ratio to the trial population as a whole is unacceptable. In addition, further recruitment in the trial or at (a) particular trial site(s) may be stopped due to insufficient compliance with the protocol, GCP and/or other applicable regulatory requirements, procedure-related problems or the number of discontinuations for administrative reasons is too high.

## 6.0 TRIAL FLOW CHART

	Screening	Week/Cycle (21-day Cycle)									Visit 10 and Beyond (21-day Cycle)	End of Treatment (EOT)  Treatment Discontinuation	Safety Follow-up 
												At time of treatment discontinuation	(30 days after EOT or prior to start of new antineoplastic therapy)
Treatment Cycle	-30 to -1	1	2	3	4	5	6	7	8	9	10-35		
Week (approximate)		0	3	6	9	12	15	18	21	24			
Scheduling Window: Days		±3	±3	±3	±3	±3	±3	±3	±3	±3	±5	+7	+7
Administrative Procedures													
Informed Consent 	X												
Inclusion/Exclusion Criteria	X												
Subject Identification Card	X (dispense)										X (collect)		
Demographics/Medical History and Prior Medications 	X												
Review Concomitant Medications		X	X	X	X	X	X	X	X	X	X	X	X
Clinical Procedures/Assessments													
Review Adverse Events		X	X	X	X	X	X	X	X	X	X	X 	
ECOG Performance Status	X 	X 	X	X	X	X	X	X	X	X	X	X	X
Physical Examination	X	X	X	X	X	X	X	X	X	X	X	X	X
Vital Signs and Weight 	X	X	X	X	X	X	X	X	X	X	X	X	X
12-Lead ECG 	X				X				X		X 	X	X
Administration of Pembrolizumab (30-min Infusion)		X	X	X	X	X	X	X	X	X	X		

	Screening	Week/Cycle (21-day Cycle)									Visit 10 and Beyond (21-day Cycle)	End of Treatment (EOT)  Treatment Discontinuation	Safety Follow-up 
												At time of treatment discontinuation	(30 days after EOT or prior to start of new antineoplastic therapy)
Treatment Cycle	-30 to -1	1	2	3	4	5	6	7	8	9	10-35		
Week (approximate)		0	3	6	9	12	15	18	21	24			
Scheduling Window: Days		±3	±3	±3	±3	±3	±3	±3	±3	±3	±5	+7	+7
Laboratory Procedures/Assessments 													
Hepatitis B and C 	X												
Pregnancy Test- Urine or Serum β-HCG 	X	X	X	X	X	X	X	X	X	X	X		
PT/INR and aPTT 	X												X
CBC With Differential 	X		X	X	X	X	X	X	X	X	X		X
Comprehensive Serum Chemistry Panel 	X		X	X	X	X	X	X	X	X	X		X
Urinalysis 	X		X			X				X	X		X
T3, FreeT4 (FT4), and TSH 	X		X		X		X		X	X	X		X
ALK Translocation Testing, NSCLC subjects only 	X												
EGFR Mutation Testing, NSCLC subjects only 	X												
Disease Assessments													
Tumor Imaging 	X				X			X		X 	X 		
Brain Imaging 	X				X					X 	X 		
Tumor Biopsies/Archival Tissue Collection													
Tumor Tissue Collection, NSCLC subjects only 	X												

	Screening	Week/Cycle (21-day Cycle)									Visit 10 and Beyond (21-day Cycle)	End of Treatment (EOT) Treatment Discontinuation	Safety Follow-up
												At time of treatment discontinuation	(30 days after EOT or prior to start of new antineoplastic therapy)
Treatment Cycle	-30 to -1	1	2	3	4	5	6	7	8	9	10-35		
Week (approximate)		0	3	6	9	12	15	18	21	24			
Scheduling Window: Days		±3	±3	±3	±3	±3	±3	±3	±3	±3	±5	+7	+7

1. Documented informed consent and audiovisual recording of the documented informed consent process must be obtained prior to performing any protocol-specific procedure. Results of a test performed as part of routine clinical management are acceptable in lieu of a screening test if performed within 30 days prior to Cycle 1, Day 1). Assign Baseline number when the study informed consent is documented.
 
2. Includes history of treatment for the primary diagnosis, including prior systemic, radiation treatment and surgical treatment, and best response to prior systemic treatments within the previous 10 years. Date of last prior cancer treatment must be documented. Radiographic studies performed prior to study entry may be collected for review by the investigator. Report complete medication history taken within 30 days prior to the screening visit (Visit 1).
 
3. All AEs should be reported for at least 30 days following treatment cessation. Serious adverse events and ECIs should be reported for 90 days following treatment cessation. A serious adverse event considered drug-related by the investigator should be reported regardless of how long has elapsed since treatment cessation. Pregnancies and lactation events should be reported for 120 days following treatment cessation or for 30 days if the subject initiates new anticancer therapy.
 
4. ECOG of 0 or 1 is required at screening and at C1D1.
 
5. Vital signs to include temperature, pulse, respiratory rate, and blood pressure. If a subject's baseline weight does not fluctuate by more than 10%, this weight can be used to calculate dose. Height will be measured at screening only.
 
6. A 12-lead ECG will be performed at Screening and at every fourth cycle starting on Cycle 4.
 
7. Routine laboratory tests (serum or plasma chemistry and hematology) for screening must be performed within 10 days prior to administration of the first dose. If a subject starts screening > 10 days prior to administration of trial treatment, a second screening visit is required to collect the lab specimens within the specified timeframe.
 
8. Testing will be performed by the local laboratory at Screening: Hepatitis B and C serologies should be obtained for subjects without a known history of hepatitis B or C. Those with a known history are ineligible. Include HCV RNA (qualitative) and HbsAg.
 
9. For females of reproductive potential, urine or serum pregnancy test should be performed within 72 hours prior to day 1 of each treatment cycle and 30 days post treatment if required or as specified per local regulatory guidance. A serum test can be done if urine is not appropriate. Additionally, if urine test is positive or is not evaluable, a serum test is required. Subjects must be excluded/discontinued in the event of a positive test result.
 
10. PT/INR and aPTT should be collected at Screening and at the Safety Follow-up Visit after discontinuation of study therapy. Coagulation parameters will be determined throughout the study if clinically indicated. PT/INR and aPTT will be analyzed by the local study site laboratory.
 
11. Routine laboratory tests (e.g., CBC with differential, comprehensive serum or plasma chemistry panel, and urinalysis) will be performed by the local study site laboratory or their contract laboratory. Additionally, CBC with differential and comprehensive serum or plasma chemistry panel are to be collected up to 48 hours prior to Day 1 dosing of any Cycle.
 
12. Following baseline and Cycle 2, urinalysis should be performed every fourth cycle.
 
13. Analysis of T3, FT4, and TSH will be performed by the local study site laboratory or their contract laboratory. Following Cycle 2, testing will be performed every other cycle.
													

	Screening	Week/Cycle (21-day Cycle)									Visit 10 and Beyond (21-day Cycle)	End of Treatment (EOT)  Treatment Discontinuation	Safety Follow-up 
												At time of treatment discontinuation	(30 days after EOT or prior to start of new antineoplastic therapy)
Treatment Cycle	-30 to -1	1	2	3	4	5	6	7	8	9	10-35		
Week (approximate)		0	3	6	9	12	15	18	21	24			
Scheduling Window: Days		±3	±3	±3	±3	±3	±3	±3	±3	±3	±5	+7	+7
14.	Tumor imaging will be performed within 30 days prior to enrollment. CT scans are the required modality for measurable disease unless a subject has a contraindication (e.g. severe contrast allergy), in which case MRI is acceptable. Premedication for contrast allergy, including steroids, is permissible. Imaging timing should follow calendar days and should not be adjusted for delays in cycle starts. Imaging should be performed 12 weeks (±7 days) after the first cycle of treatment and then every 9 weeks (±7 days), or as clinically indicated. Brain MRI should be performed at screening, 12 weeks (±7 days) after the first cycle of treatment, and then every 18 weeks (±7 days), or as clinically indicated. For subjects for whom an MRI is contraindicated, brain CT scan is acceptable. In subjects who discontinue trial treatment, tumor imaging should be performed at the time of treatment discontinuation (± 4 week window). If a previous scan was obtained within 4 weeks prior to the date of discontinuation, then a scan at treatment discontinuation is not mandatory. This is the final required tumor imaging.												
15.	This test is only required for NSCLC subjects (1 st line, 2 nd line, and beyond treatment subjects). This test is not required for melanoma subjects. Site must be able to provide documentation of the subject's tumor EGFR mutation and ALK translocation status. If the site is unable to provide this source documentation, then the Sponsor will offer this molecular testing of the tumor.												
16.	Tumor tissue from NSCLC subjects only (1 st line, 2 nd line, and beyond treatment subjects) for biomarker analysis from an archival tissue sample (acceptable for EGFR and ALK testing) or newly obtained formalin fixed tumor tissue from a recent biopsy of a tumor lesion not previously irradiated (required for PD-L1 determination; acceptable for EGFR and ALK testing) must be provided and evaluated by the laboratory before randomization. No systemic antineoplastic therapy may have been received by the subject between the time of the biopsy for PD-L1 testing and the first administration of study medication. Detailed instructions for tissue collection, processing and shipment are provided in the Procedures Manual. Biopsy should be obtained of a non-target lesion, but if obtained from a target lesion then a new baseline scan should be acquired.												
17.	EOT and Safety Follow-up visits may be combined if a decision is made to end treatment 30 or more days since the last dose of treatment.												

## **7.0 TRIAL PROCEDURES**

### **7.1 Trial Procedures**

The Trial Flow Chart - Section 6.0 summarizes the trial procedures to be performed at each visit. Individual trial procedures are described in detail below. It may be necessary to perform these procedures at unscheduled time points if deemed clinically necessary by the investigator.

Furthermore, additional evaluations/testing may be deemed necessary by the investigator and or the Sponsor for reasons related to subject safety. In some cases, such evaluation/testing may be potentially sensitive in nature (e.g., HIV, Hepatitis C, etc.), and thus local regulations may require that additional informed consent be obtained from the subject. In these cases, such evaluations/testing will be performed in accordance with those regulations.

#### **7.1.1 Administrative Procedures**

##### **7.1.1.1 Informed Consent**

The investigator or qualified designee must obtain documented consent from each potential subject or each subject's legally acceptable representative prior to participating in a clinical trial. If there are changes to the subject's status during the trial (e.g., health or age of majority requirements), the investigator or qualified designee must ensure the appropriate consent is in place.

An audio-video recording of the informed consent process shall be maintained by the Investigator for record if required by applicable regulatory guidelines. Sufficient measures will be taken to maintain the confidentiality of the recordings of the trial subjects.

###### **7.1.1.1.1 General Informed Consent**

Consent must be documented by the subject's dated signature or by the subject's legally acceptable representative's dated signature on a consent form along with the dated signature of the person conducting the consent discussion.

A copy of the signed and dated consent form should be given to the subject before participation in the trial.

The initial informed consent form, any subsequent revised written informed consent form and any written information provided to the subject must receive the IRB/ERC's approval/favorable opinion in advance of use. The subject or his/her legally acceptable representative should be informed in a timely manner if new information becomes available that may be relevant to the subject's willingness to continue participation in the trial. The communication of this information will be provided and documented via a revised consent form or addendum to the original consent form that captures the subject's dated signature or by the subject's legally acceptable representative's dated signature.

Specifics about a trial and the trial population will be added to the consent form template at the protocol level.

The informed consent will adhere to IRB/IEC requirements, applicable laws and regulations and Sponsor requirements.

### **7.1.1.2 Inclusion/Exclusion Criteria**

All inclusion and exclusion criteria will be reviewed by the investigator or qualified designee as well as the Sponsor to ensure that the subject qualifies for the trial prior to enrollment.

### **7.1.1.3 Subject Identification Card**

All subjects will be given a Subject Identification Card identifying them as participants in a research trial. The card will contain trial site contact information (including direct telephone numbers) to be utilized in the event of an emergency. The investigator or qualified designee will provide the subject with a Subject Identification Card immediately after the subject provides documented informed consent. At the time of treatment allocation/randomization, site personnel will add the treatment/randomization number to the Subject Identification Card.

The subject identification card also contains contact information for the emergency unblinding call center so that a health care provider can obtain information about trial medication/vaccination in emergency situations where the investigator is not available.

### **7.1.1.4 Medical History**

A medical history will be obtained by the investigator or qualified designee.

Medical history will include all active conditions, and any condition diagnosed within the previous 10 years that are considered to be clinically significant by the investigator. Disease details regarding the subject's melanoma or NSCLC will be recorded separately and not listed as medical history.

#### **7.1.1.4.1 Subsequent Antineoplastic Therapy Status**

The investigator or qualified designee will review all new antineoplastic therapy initiated after the last dose of trial treatment. If a subject initiates a new antineoplastic therapy within 30 days after the last dose of trial treatment, the "30-day Safety Follow-up visit" should occur prior to starting the new antineoplastic therapy.

### **7.1.1.5 Prior and Concomitant Medications Review**

#### **7.1.1.5.1 Prior Medications**

The investigator or qualified designee will review prior medication use, including any protocol-specified washout requirement, and record prior medication taken by the subject within 30 days before first dose of trial medication.

#### **7.1.1.5.2 Concomitant Medications**

The investigator or qualified designee will record medication, if any, taken by the subject during the trial. All concomitant medication will be recorded on the eCRF, including all prescription, OTC, herbal supplements, and IV medications and fluids. If changes occur

during the study period, documentation of drug dosage, frequency, route, and date will also be included on the eCRF.

#### **7.1.1.6 Assignment of Screening Number**

All consented subjects will be given a unique screening number that will be used to identify the subject for all procedures that occur prior to treatment allocation. Each subject will be assigned only one screening number. Screening numbers must not be re-used for different subjects.

Any subject who is screened multiple times will retain the original screening number assigned at the initial screening visit.

#### **7.1.1.7 Assignment of Treatment/Randomization Number**

All eligible subjects will be allocated, by non-random assignment, and will receive a treatment number. The treatment number identifies the subject for all procedures occurring after treatment allocation. The assigned screening number will become the subject's treatment number. Once a treatment number is assigned to a subject, it can never be re-assigned to another subject.

A single subject cannot be assigned more than 1 treatment number.

#### **7.1.1.8 Trial Compliance (Medication/Diet/Activity/Other)**

Interruptions from the protocol specified treatment for >12 weeks require consultation between the investigator and the Sponsor and written documentation of the collaborative decision on subject management.

See Section 7.1.2.6.

### **7.1.2 Clinical Procedures/Assessments**

#### **7.1.2.1 Review Adverse Events**

The Investigator or qualified designee will assess each subject to evaluate for potential new or worsening AEs specified in the Trial Flow Chart (Section 6.0) and more frequently, if clinically indicated. Adverse experiences will be graded and recorded throughout the trial and during the follow-up period as defined by CTCAE, Version 4.0 (see [Section 12.4]). Toxicities will be characterized in terms regarding seriousness, causality, toxicity grading, and action taken with regard to trial treatment.

All AEs of unknown etiology associated with pembrolizumab exposure should be evaluated to determine if it is possibly an event of a potentially immunologic etiology; see Section 5.6.1 regarding the identification, evaluation, and management of AEs of a potential immunological etiology.

Please refer to Section 7.2 for detailed information regarding the assessment and recording of AEs. Subjects should be assessed for possible ECIs prior to each dose. Laboratory results should be evaluated and subjects should be asked for signs and symptoms suggestive of an immune-related adverse event. Subjects who develop an adverse event thought to be immune-related should have additional testing to rule out other etiologic causes. If laboratory

results or symptoms indicate a possible immune-related adverse event, then additional testing should be performed to rule out other etiologic causes. If no other cause is found, then it is assumed to be immune-related.

#### **7.1.2.2 Eastern Cooperative Oncology Group Performance Status**

The investigator or qualified designee will assess ECOG Performance Status (see [Section 12.5]) at screening, prior to dosing on Day 1 of each treatment cycle, at EOT, and during the safety follow up, as specified in the Trial Flow Chart (Section 6.0).

#### **7.1.2.3 Physical Examination**

The investigator or clinical designee will perform a complete physical examination during the screening period, Day 1 of each cycle, EOT, and the 30-day safety follow-up visit. Clinically significant abnormal findings should be recorded as medical history. Additional full physical examinations should be performed as specified in the Trial Flow Chart (Section 6.0). After the first dose of trial treatment new clinically significant abnormal findings should be recorded as AEs.

#### **7.1.2.4 Vital Signs and Weight**

Vital sign measurements include blood pressure, pulse, respiratory rate, body temperature, and weight. Height will be measured at screening only.

#### **7.1.2.5 12-Lead Electrocardiograms**

Baseline ECGs will be obtained at screening, with additional ECGs obtained every fourth cycle, starting on Cycle 4 Day 1, EOT, the safety follow-up visit and as clinically indicated for all subjects. Clinically significant abnormal findings found at screening should be recorded as medical history. Clinically significant abnormal findings after the screening ECG must be recorded as an adverse event.

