### **7.2 Assessing and Recording Adverse Events**

An adverse event is defined as any untoward medical occurrence in a patient or clinical investigation subject administered a pharmaceutical product and which does not necessarily have to have a causal relationship with this treatment. An adverse event can therefore be any unfavourable and unintended sign (including an abnormal laboratory finding, for example), symptom, or disease temporally associated with the use of a medicinal product or protocol-specified procedure, whether or not considered related to the medicinal product or protocol-specified procedure. Any worsening (i.e., any clinically significant adverse change in frequency and/or intensity) of a preexisting condition that is temporally associated with the use of the Sponsor's product, is also an adverse event.

Changes resulting from normal growth and development that do not vary significantly in frequency or severity from expected levels are not to be considered adverse events. Examples of this may include, but are not limited to, teething, typical crying in infants and children and onset of menses or menopause occurring at a physiologically appropriate time.

Sponsor's product includes any pharmaceutical product, biological product, device, diagnostic agent or protocol-specified procedure, whether investigational (including placebo or active comparator medication) or marketed, manufactured by, licensed by, provided by or distributed by the Sponsor for human use.

Adverse events may occur during clinical trials, or as prescribed in clinical practice, from overdose (whether accidental or intentional), from abuse and from withdrawal.

Progression of the cancer under study is not considered an adverse event.

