All adverse events that occur after the consent form is signed but before treatment allocation/randomization must be reported by the investigator if they cause the subject to be excluded from the trial, or are the result of a protocol-specified intervention, including but not limited to washout or discontinuation of usual therapy, diet, placebo treatment or a procedure. From the time of treatment allocation/randomization through 30 days following cessation of treatment, all adverse events must be reported by the investigator. Such events will be recorded at each examination on the Adverse Event case report forms/worksheets. The reporting timeframe for adverse events meeting any serious criteria is described in section 7.2.3.1. The investigator will make every attempt to follow all subjects with non-serious adverse events for outcome.

Electronic reporting procedures can be found in the Electronic Data Capture (EDC) data entry guidelines. Paper reporting procedures can be found in the Investigator Trial File Binder (or equivalent).

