## 8.5 Analysis Populations

### 8.5.1 Safety Analysis Populations

The All Subjects as Treated (ASaT) population will be used for the analysis of safety data in this study. The ASaT population consists of all subjects who received at least 1 dose of trial treatment.

At least 1 laboratory or vital sign measurement obtained subsequent to at least 1 dose of trial treatment is required for inclusion in the analysis of each specific parameter. To assess change from baseline, a baseline measurement is also required.

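### The ECG recording rule makes no comparison with the screening ECG, so a persistent baseline abnormality can also be entered as an on-treatment adverse event

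*Combined protocol and SAP*

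**What the plan says.** Section 7.1.2.5 handles ECG findings in two consecutive sentences. For the screening ECG: "Clinically significant abnormal findings found at screening should be recorded as medical history". For everything later: "Clinically significant abnormal findings after the screening ECG must be recorded as an adverse event".

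Three other places deal with the same question.

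- Section 7.1.2.1, on AE review, says the investigator "will assess each subject to evaluate for potential new or worsening AEs specified in the Trial Flow Chart".
- Section 7.1.2.3, on physical examination, says: "After the first dose of trial treatment new clinically significant abnormal findings should be recorded as AEs".
- Section 7.2, in the AE definition, brings in a pre-existing condition through "Any worsening (i.e., any clinically significant adverse change in frequency and/or intensity) of a preexisting condition". It does not name an unchanged condition as an AE.

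The general collection window is in Section 7.2: "From the time of treatment allocation/randomization through 30 days following cessation of treatment, all adverse events must be reported by the investigator". On the schedule, the Section 6.0 footnote says: "A 12-lead ECG will be performed at Screening and at every fourth cycle starting on Cycle 4". Section 7.1.2.5 adds ECGs at end of treatment and at safety follow-up.

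In the analysis plan, Section 8.5.1 says: "The ASaT population consists of all subjects who received at least 1 dose of trial treatment". Section 8.6.1 and Table 8 then summarise AEs by subject. They state no treatment-emergent rule and no comparison of a recorded AE with baseline.

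**The concern.** The ECG sentence is mandatory and is the only one of the four rules without a baseline comparison. A subject whose screening ECG shows a clinically significant abnormality has it entered in medical history. If the Cycle 4 ECG shows the same thing, the literal wording also requires an AE. A site that applies the definition in Section 7.2 would record nothing. Both are reasonable ways to follow the protocol, so the count depends partly on which reading a site takes.

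The AE experience is the primary endpoint (Section 8.1), and there is no comparator (Section 4.2.2.1). In a controlled trial, a recording habit of this kind would tend to appear in both arms. Here nothing would expose it. Once entered, the event goes into the tables like any other AE.

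**Working it through.** **1. The rules side by side.**

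| Section | Baseline comparison | Start of the rule |
|---|---|---|
| 7.1.2.1 AE review | new or worsening | visits in the flow chart |
| 7.1.2.3 Physical examination | new | after first dose |
| 7.2 AE definition and window | worsening of a pre-existing condition | allocation, with limited reporting before it |
| 7.1.2.5 ECG | none stated | after the screening ECG |

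**2. Is there a correction downstream?** Sections 8.5.1 and 8.6.1 contain none. Table 8 has a change-from-baseline row that includes ECGs. It is a separate descriptive summary and does not affect AE counts.

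**3. Opportunities for the issue to arise.** Scheduled on-treatment ECGs fall at Cycles 4, 8, 12, 16, 20, 24, 28 and 32, which is 8. End of treatment and safety follow-up make 8 + 2 = 10. This is a maximum: it needs treatment to Cycle 32 and separate final visits, which Section 6.0 allows to be combined. Repeats do not multiply the subject-level count.

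**4. The plan's own intervals.** The exact 95% interval for x of n subjects has limits Beta(0.025; x, n − x + 1) and Beta(0.975; x + 1, n − x). With n = 150 this reproduces all seven rows of Section 8.9.1. For example, 8/150 gives 2.3% to 10.2% and 15/150 gives 5.7% to 16.0%. The point about ECG wording does not depend on these figures.

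**5. Illustration for ECG AEs taken together.** Two inputs are assumed, because the documents supply neither: 3 of 150 subjects have a truly new finding, and 2%, 5% or 10% have a clinically significant abnormality at screening. Every such abnormality is taken to be re-recorded in a subject without a new finding.

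| Assumed frequency at screening | Re-recorded | Reported with an ECG AE | 95% CI |
|---|---|---|---|
| 0% | 0 | 3/150 = 2.0% | 0.4% to 5.7% |
| 2% | 3 | 6/150 = 4.0% | 1.5% to 8.5% |
| 5% | 8 (7.5 rounded) | 11/150 = 7.3% | 3.7% to 12.7% |
| 10% | 15 | 18/150 = 12.0% | 7.3% to 18.3% |

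With a new-or-worsened condition the result stays at 3/150.

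**6. Table 8 cut.** The 1% threshold is 0.01 × 150 = 1.5 subjects. Two re-recorded findings under one term are therefore enough to move it into the rows reported with an interval.

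**7. Any AE.** If a proportion p have an AE for other reasons, and a proportion q have an abnormality re-recorded independently of that, the rise is (1 − p) × q. With p assumed between 70% and 95% and q between 2% and 10%, it runs from 0.05 × 0.02 = 0.1 points to 0.30 × 0.10 = 3.0 points.

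**The case against.** The best defence is that the two ECG sentences form a pair: a finding is classified by when it is first found, so one already in medical history has been dealt with. Section 7.1.2.1 looks for new or worsening events and refers to Section 7.2 for detail, and a procedure paragraph does not displace the AE definition. This reading is fair. It means the sections can be reconciled, and that the ECG sentence is too broad rather than in outright conflict with them. It does not make the ECG sentence say so, and a site that applies it as written is not in error.

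Several stronger readings are tempting and are not supported.

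- A reader might infer that the protocol orders unchanged findings to be counted as AEs. It never says that; the literal wording only reaches that far.
- A reader might take the illustrative rates as an estimate. No frequency of screening abnormalities is given, different abnormalities would spread over several terms, and Exclusion 22 may keep some such subjects out. The table also assumes that every site takes the literal reading.
- A reader might see the missing first-dose start as a further serious fault. The first scheduled post-screening ECG is at Cycle 4, and Section 7.2 already sets an allocation start. Only an unscheduled ECG between screening and allocation would be affected.
- A reader might connect this to myocarditis in Table 4. An unchanged baseline ECG finding is not myocarditis, and Table 4 calls for evaluation of cause.

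It also stands that the trial is descriptive, with no hypothesis test at risk, and that the change-from-baseline summaries could show persistence.

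**Conclusion.** The point holds as a wording defect with a limited consequence. Section 7.1.2.5 is broader than the protocol's other AE rules, so persistent screening abnormalities can be recorded as on-treatment AEs, and sites may differ in whether they do it. Nothing in Section 8 corrects this. The effect would fall mainly on ECG and cardiac AE rows. Its size there cannot be derived from the documents, and the rates shown above rest entirely on assumed frequencies. On any-AE it is likely small, at about 0.1 to 3.0 points under the stated assumptions. The documents do not show that any such event has been recorded. The correction is worth making because it is cheap and makes capture of the primary endpoint more uniform.

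**What to change.** Replace the sentence in Section 7.1.2.5 with: *Clinically significant ECG findings that are new or worsened compared with the screening ECG must be recorded as adverse events, within the reporting period in Section 7.2.* This keeps the allocation start of Section 7.2. A separate first-dose start for ECGs would remove one inconsistency and add another.

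Before database lock, list ECG-related AEs that match a finding on the same subject's screening ECG or in medical history. Query the site so that the investigator can confirm or correct the entry. Do not remove recorded AEs from Table 8 by a sponsor rule: in an open-label safety trial, taking out investigator-reported events after collection would be harder to defend than the over-count it is meant to cure.

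The cost is one amendment sentence and one data query.
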